5.2.2.2 Summary Measures

See 5.1.1

5.2.2.3 Assumption Checks

A logistic regression includes the following assumptions:

- Binary dependent variable: This assumption is fulfilled trough the study design. OMERACT/OARSI responder criteria, calculated into a binary yes or no score.
- Independence: This assumption is fulfilled through the study design.
- No severe multicollinearity: This assumption is fulfilled through the study design.
- Sufficient number of observations: The sample size was calculated based on approximately 20% responders in the control group and 40% responders in the intervention group, which would provide sufficient number of patients per group.

A linear regression includes the following assumptions:

- Continuous dependent variable: This assumption is fulfilled through the study design.
- Independence: This assumption is fulfilled through the study design.
- Homoscedasticity: The spread of the residuals should be roughly the same across the regression line and should rather not exceed +3 and -3.
- ٠

Statistical Analysis Plan Happy Hands Diakonhjemmet Hospital

Page 24 of 27

• Multicollinearity: The independent variables should not be highly correlated (r<0.7)

In case the outcome variable or the residuals are severly skewed, transformation (eg logtransformation) of the outcome variable will be carried out.

5.2.2.4 Missing Data

We are expecting the amount of missing data to increase with time, but we cannot retrace the individual reasons for missingness. The cost-effectiveness analysis will utilize multiple imputation for missing whole questionnaires of EQ-5D. Costs will be assumed to be missing if the whole questionnaire is missing. If the questionnaire is answered without reporting costs, it will be assumed that the costs are 0. The other secondary analyses will be based on complete case analysis.

5.2.2.5 Sensitivity Analyses

If deemed necessary, sensitivity analyses will also be conducted to address missing data and subgroup data.

5.2.2.6 Subgroup Analyses

No subgroup analyses are planned outside of the sensitivity analyses.

5.2.3 Additional Analyses

5.2.3.1 Exploratory Analyses

The following additional, hypothesis-generating, exploratory analyses will be conducted in addition to the above-stated analyses. If additional questions/analyses are raised during the analysis process, we will add them to this list of exploratory analyses.

- a) To assess the adherence, satisfaction and usability with use of the Happy Hands app, we will only include participants allocated to the intervention group. Adherence will be described with mean and SD or median and interquartile range, as well as the proportion of participants with adequate adherence to the exercise sessions and the information videos. Satisfaction and usability will be described with mean and SD or median and interquartile range.
- b) To identify relevant factors associated with being an OMERACT/OARSI responder at 3 and 6 months we will use multiple logistic regression and select variables based previous research and clinical relevance.
- c) To identify factors associated with adherence to the interventions (exercise and information videos) in the Happy Hands app, both multiple linear and logistic regression may be used.

6. Safety Analyses

6.1 Adverse Events/Safety

AEs is based on self-report in open-ended questions in the 3-months follow-up questionnaire and emails or phone calls from patients and will be categorised as mild to moderate depending on the

> Statistical Analysis Plan Happy Hands Diakonhjemmet Hospital

Page 25 of 27

description in the questionnaire. Brief transitory pain/discomfort will be regarded as mild AEs and persistent pain/discomfort will be considered moderate AEs.

Per definition, any events caused by the intervention that results in significant disability, prolonged hospitalization, life threatening events or death are categorized as serious adverse events (SAE). As we did not expect that the intervention would cause any SAEs, we did not ask the patients for permission to retrieve information from their medical journal. Thus, information on life threatening events or death are not included in the study. Participants were asked about surgery and hospitalization due to hand osteoarthritis, however, planned surgery will not be considered an AE/SAE as this may be part of the treatment for these patients.

7. Statistical Software

All data handling and statistical analyses will be performed using Stata (*StataCorp. 2015. College Station, TX, USA*).

8. Ethics

The project is granted approval by the Regional Committees for Medical and Health Research Ethics (REK) in Norway (REK no 477746)

The study is funded by the Dam Foundation (2022/FO387170). The funders have no role in the study other than providing funding.

Data is stored in Services for sensitive data (TSD) at the University of Oslo and in a secure research server at Diakonhjemmet Hospital.

9. References

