5.1.4 Overview of Outcomes

Table 1 Primary and secondary outcomes

	Data collection instrument and scale	Timepoints
Primary outcome		
Probability of OMERACT- OARSI response	The responder classification is a composite index reported as a single variable (yes/no)	t0, mo, t3, t6
·		
Secondary outcomes		
Hand pain at rest	Pain left/right hand last week, NRS 0-10, 0= no pain	t0, ex, mo, t3, t6
Pain in activity	Pain left/right hand last week, NRS 0-10, 0= no pain	t0, ex, mo, t3, t6
Stiffness	Stiffness left/right hand last week, NRS 0-10, 0= no stiffness	t0, ex, mo, t3, t6
Grip strength	Maximum grip strength, mean of two measures left/right hand, in kg using the JAMAR dynamometer	t0, t3
Activity performance of the hands (hand function)	Measured by the Measure of Activity Performance of the Hand (MAP-Hand); mean of 18 standardized activities, rating scale 1 ("no difficulty") to 4 ("cannot perform")	t0, mo, t3, t6
Health-related quality of life	Measured by EuroQoI EQ-5D-5L, five items (mobility, self-care, usual activities, pain/discomfort, anxiety/depression) scored at five level scare ("no problems" to "unable to do"), calculated as an utility index 0-1, 1= best health-related quality of life. Visual analogue scale (EQ VAS), 0-100, 100= perfect health	t0, t3, t6 a
Global assessment of disease activity	Disease activity last week, NRS 0-10, 0=no disease activity	t0, mo, t3, t6
Global assessment of change	5-point Likert scale from "Much better" to "Much worse"	t3, t6
Quality of care	Modified version of the OsteoArthritis Quality Indicator questionnaire, 15 questions rated as yes/no/unsure or not applicable, scored as pass rate 0-100, 100=best quality of care	t0, t3, t6
Motivation for hand exercises	NRS 0-10, 10=highly motivated	t0, t3, t6
	Statistical Analysis Plan	
	Happy Hands Pa Diakonhiemmet Hospital	age 19 of 27

Hand exercises	Approximately number of exercise sessions each week for the last 3 months	t3, t6
Costs		
Healthcare use	Number of consultations with healthcare providers last 3 months	t3, t6
Medication use	Type and dosage last 3 months	t0, t3, t6
Hand surgery	Conducted hand surgery last 3 months (yes/no), if yes, reported sick leave due to hand surgery	t3, t6
Hospitalization	Number of hospital admissions	t3, t6
Medical equipment	Any medical equipment (i.e. hand orthoses, exercise equipment) bought last 3 months (type and cost)	t3, t6

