Technical equipment	Any technical equipment (i.e. bread knife, jar key, sissors, electric toothbrush) bought last 3 months (type and cost)	t3, t6
Work status	Reported as yes/no on the following options: working, sick leave, retired, disability pension, work assessment allowance, unemployed, not working, student	t0, t3, t6
Use of the Happy Hands app (inte Usability	ervention group only) Measured by System Usability Scale (SUS), 10 statements scored on a 5-point scale from "strongly disagree" to "strongly agree"	t3, t6
Satisfaction with use of the	NRS 0-10, 10=highly satisfied	t3, t6
Usefulness of the app	NRS 0-10, 10=highly useful	t3, t6
Adherence to hand	Number of exercises conducted	t3, (t6)
exercises Adherence to informational videos	Number of informational videos watched	t3, (t6)
Adherence to quizzes	Number of quizzes answered	t3
Continued use	Plans to continue using the app, measured as yes/no/unsure	t3, t6
Adverse events	Description of any complaints related to hand exercises	t3
Baseline characteristics		
Age	Years	t0
Gender	Female, male, other	t0
Living arrangement	Living alone, living together with someone	t0
Education	Elementary school, high school, university/college <4 years, university/college > 4 years	t0
Smoking	No previously ves	t0
Height	Cm	t0
Weight	Kø	t0
Most troublesome hand	left right hoth	t0
Other painful joints	Hin knee foot/ankle	t0
Previous treatment for HOA	Yes no	t0
Previous hand surgery	Yes no	t0
Comorbidities	,	
	High blood pressure, heart disease, lung disease, allergy, back pain, stroke, cancer, neurological disease, diabetes, metabolic disease, mental disease, kidney disease, liver disease, ulcer, blood disease	tO

Statistical Analysis Plan Happy Hands Diakonhjemmet Hospital

Page 20 of 27

Health Literacy	eHEALS, 5-point scale with a total score ranging from 8 to 40 (higher score representing higher health literacy)	t0
Experience with using technology and digital services	Experience with smartphone, tablets, apps, video consultation, and digital services (Helsenorge.no), measured on a 5-point scale (very poorly to very good) with an additional alternative of 'never tried'	t0
Motivation for digital treatment/follow-up	NRS 0-10, 10=to a large degree	t0

t0=baseline; t3=3 months; t6=6 months; ex=after each exercise session (in the app/intervention group only); mo=monthly (in the app/intervention group only); NRS=numeric rating scale; MAP-Hand=Measure of Activity Performance of the Hand; HOA=hand osteoarthritis

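### The adverse event count cannot show harm relative to usual care: who is asked is unclear, events are graded by pain alone, and no between-arm comparison of worsening is planned

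*SAP*

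**What the plan says.** SAP section 5.1.4, Table 1, defines the adverse event item as "Description of any complaints related to hand exercises". Its only time point is 3 months, and it stands in the block on app use, whose heading restricts it to the intervention group.

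Section 6.1 describes the sources differently: "AEs is based on self-report in open-ended questions in the 3-months follow-up questionnaire and emails or phone calls from patients". No arm is named. Severity depends only on how long pain lasts: "Brief transitory pain/discomfort will be regarded as mild AEs", and "persistent pain/discomfort will be considered moderate AEs". Serious adverse events are "any events caused by the intervention that results in significant disability, prolonged hospitalization, life threatening events or death". The section adds that participants were asked about surgery and hospitalisation, and that planned surgery will not count as an event. It gives no denominator, summary measure or comparison between arms.

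Other harm-related data are listed outside the intervention-only block:
- pain NRS at baseline, 3 and 6 months (section 5.1.1.15 and Table 1)
- global assessment of change, on a five-point scale that runs to much worse, at 3 and 6 months (Table 1)
- hand surgery and hospital admissions at 3 and 6 months (Table 1)

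Section 5.2.2.1(c) names pain, hand function, grip strength, disease activity and quality of care for analysis. Global change is not among them.

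**The concern.** Pain in the hand is what these patients have at entry, and it is a component of the primary outcome (section 5.1.2). A count of painful complaints without a control count mixes pain provoked by the exercises with the ordinary course of the disease. The definition of serious events has the same weakness. It requires a causal judgement on each case, and a usual-care participant cannot have such an event by definition.

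The planned efficacy analyses do not fill the gap. The responder rule puts unchanged and worse patients together as non-responders. Mean change lets improvement in some patients offset deterioration in others. A benefit on average could therefore coexist with a minority made worse, and no planned table would show it. Section 1.1 presents the app as a standalone intervention, so what the trial can say about harm matters to those who would adopt it.

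**Working it through.** **1. Who is asked.** Table 1 puts the solicited question in the intervention-only block. Section 6.1 refers to the 3-month questionnaire and to unsolicited contacts from patients in general. On Table 1, controls do not get the question. On section 6.1 alone, they might. The SAP does not settle it.

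**2. What existing analyses show about worsening.**

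| Data listed for both arms | Planned use | Shows worsening by arm? |
|---|---|---|
| Pain NRS (baseline, 3, 6 months) | responder rule; mean change | no: pooled with unchanged, or averaged |
| Global change (3, 6 months) | not named in 5.2.2.1(c) | no |
| Hand surgery, admissions (3, 6 months) | costs; mentioned in 6.1 | no comparison stated |

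**3. Size of the problem, as an illustration.** The SAP states no adverse event or worsening rate, so there is no figure to reproduce and the rates below are assumptions. The inputs are 376 patients in total and 25% drop-out (section 2.3), and 1:1 allocation (section 2.2).

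- Per arm: 376 / 2 = 188
- Followed up per arm: 188 × 0.75 = 141
- Moderate events with no true excess = 141 × assumed rate of natural worsening

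| Assumed rate | Moderate events in the app arm |
|---|---|
| 10% | 141 × 0.10 ≈ 14 |
| 15% | 141 × 0.15 ≈ 21 |
| 20% | 141 × 0.20 ≈ 28 |
| 30% | 141 × 0.30 ≈ 42 |

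This assumes that every patient who worsens reports it as an exercise complaint. The item asks only for such complaints, so each figure is an upper bound.

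**4. Precision of a between-arm comparison.** The half-width of the 95% interval for a risk difference is 1.96 × √{[p₁(1−p₁) + p₂(1−p₂)] / n}. Assume 15% worsening with usual care and 25% with the app. Take n = 145 per arm, between the 141 above and the 150 per group in section 2.3:

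- 1.96 × √[(0.1275 + 0.1875) / 145] = 1.96 × 0.0466 ≈ 0.091
- with n = 141 the result is 0.093, and with n = 150 it is 0.090

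With equal rates of 10%, 20% or 30% in both arms and 141 per arm, the half-width is about 7, 9 or 11 percentage points. The excess detectable with 80% power at two-sided 5% is about 12, 15 or 16 points.

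**The case against.** A reader might infer that adverse events are collected only in the app arm. The SAP does not establish this. The restriction rests on one table heading; section 6.1 names no arm, and emails or calls could come from either arm at any time. What stands is that the two places need reconciling, and that unsolicited contacts in an open-label trial are not a comparable control count.

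The item asks for complaints linked to hand exercises, so patients make some attribution themselves. That is fair, and it is why the illustration is an upper bound. Attribution by the patient is still not a comparator.

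The SAP sets no comparative safety objective or hypothesis and nowhere claims that the app is safe relative to usual care. This is correct: no planned test is wrong. The gap lies in what section 6 leaves the trial able to say.

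Pain is already compared between arms as mean change, and patients who deteriorate contribute to those means. This stands as far as it goes, but a mean does not give the proportion made worse.

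It is tempting to criticise the absence of the question at 6 months. The intervention lasts 12 weeks and the 3-month question covers it, so this gap is secondary and concerns mainly continued use and late complaints.

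Finally, the proposed comparison uses the same 3- and 6-month questionnaires and so shares their missing data. Its self-reports are open-label, and last-week pain ratings cannot capture transient pain. These limits are real.

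**Conclusion.** The point holds in this form: the SAP is unclear about which arm gets the adverse event question, and its planned harm data have no comparator although both arms supply information on worsening. The primary analysis is not affected.

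The documents do not support a claim that the app causes harm, or that any particular number of events will be miscounted. The figure of about 21 rests on an assumed 15% natural worsening, 141 patients followed up and complete attribution to the exercises. Applying 15% to all 188 allocated patients would give about 28, but the question reaches only those who return the 3-month form, so that larger figure does not follow under the planned 25% loss.

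A by-arm comparison with a half-width near 9 points would be informative but could not exclude a moderate excess of worsening.

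**What to change.** Reconcile Table 1 with section 6.1 by stating which arm or arms receive the adverse event question. Then add to section 6.1 a descriptive comparison by arm at 3 and 6 months, as risk differences with 95% confidence intervals:

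- (a) the proportion in the worse categories of global assessment of change;
- (b) the proportion whose pain NRS rises by at least 2 points, on the same pain score that the responder rule uses. Section 5.1.1.15 records pain for each hand at rest and in activity (2 × 2 = 4 scores), and section 5.1.2 does not say which one applies, so the SAP must name it in advance;
- (c) hand surgery and hospital admissions, without reclassifying planned surgery as an event.

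Handle missing 3- and 6-month questionnaires with the multiple imputation planned for the primary outcome (section 5.2.1.5). Its model should also include global change and the 6-month values. Show the number observed per arm beside each estimate. State that app-arm exercise complaints are reported descriptively and do not support a conclusion of safety relative to usual care.

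The cost is a few lines and two by-arm tables, with no new data collection. The 2-point cut-off is a choice: the responder rule pairs it with at least 50% change, which is not carried over here. It should be fixed before the data are examined.

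### SAP section 6.1 counts a serious adverse event only if the app caused it, and lists outcomes the study does not collect, so a report of no SAEs would say little about safety

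*SAP*

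**What the plan says.** Section 6.1 of the SAP holds the whole safety analysis.

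- **Source.** It says that "AEs is based on self-report in open-ended questions in the 3-months follow-up questionnaire and emails or phone calls from patients".
- **Grading.** AEs "will be categorised as mild to moderate", according to the patient's description. Short-lived discomfort is mild and persistent discomfort is moderate.
- **Seriousness.** The rule is that "any events caused by the intervention that results in significant disability, prolonged hospitalization, life threatening events or death are categorized as serious adverse events".
- **Records.** The section gives its reason, "As we did not expect that the intervention would cause any SAEs", for not having sought consent to consult medical records. It concludes that "information on life threatening events or death are not included in the study".
- **Surgery and hospital stays.** Participants were asked about these in connection with hand osteoarthritis. Planned surgery is not to count as an AE or SAE.

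Table 1 (section 5.1.4) lists "Number of hospital admissions" and hand surgery at 3 and 6 months, both under costs. Its adverse-event row asks about complaints related to hand exercises, at 3 months only, and appears to belong to the block for app users.

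**The concern.** Seriousness describes the outcome of an event, and relatedness describes its cause. Section 6.1 merges the two. Once cause is part of the definition, the control arm has no SAE count to set beside that of the app arm, and randomisation can no longer show whether serious events are more common with the app. The definition also names outcomes that the same section says were not collected.

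What is at stake is how the safety statement will be read. The app is meant as a standalone intervention (section 1.1). A sentence saying that no SAEs occurred would be taken as evidence that it is safe, although much of that result would come from the definition and from what was collected.

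**Working it through.** The plan gives no figure here to reproduce. The check sets its statements side by side and then adds one illustration.

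**Step 1: who can have an SAE.** Control participants receive usual care alone (section 2.1), and the app link goes only to the intervention group (section 2.2). An event in the control arm cannot have been caused by the app, so the control-arm SAE count is 0 by definition.

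**Step 2: the four criteria against the data sources.**

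| Criterion in 6.1 | Source in the SAP | App arm | Control arm |
|---|---|---|---|
| Death | None; stated as not included | Always 0 | Always 0 |
| Life-threatening event | None; stated as not included | Always 0 | Always 0 |
| Prolonged hospitalization | Self-report; admissions item at 3 and 6 months | Possible, if attributed to the app | 0 by definition |
| Significant disability | Free-text self-report, emails, calls | Possible, if attributed to the app | 0 by definition |

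Of the eight cells, six are fixed at zero and two are open.

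**Step 3: grading.** The two grades separate brief from persistent discomfort. An intense event that meets no seriousness criterion can be graded no higher than moderate.

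**Step 4: hospital admissions.** Section 6.1 describes the question as concerning hospitalization due to hand osteoarthritis. Table 1 gives a number of admissions and states no such limit. These describe different data, and the SAP does not say which was collected. Table 1 also lists a count without length of stay, and hand surgery without a planned/unplanned marker.

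**Step 5: how little a zero says (illustration only).** Let r be the true risk of an SAE in the app arm and c the chance that such an event is captured and attributed. Neither is in the documents, so both are assumed over a range. One arm has N = 376/2 = 188 participants, before drop-out. Then

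P(no SAE recorded) = (1 − r × c)^188

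| r | c = 1 | c = 0.5 | c = 0.25 | c = 0 |
|---|---|---|---|---|
| 0.5% | 0.390 | 0.625 | 0.790 | 1.000 |
| 1% | 0.151 | 0.390 | 0.625 | 1.000 |
| 2% | 0.022 | 0.151 | 0.390 | 1.000 |

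The last column is the position for death and life-threatening events. For the other two criteria, c is above 0 but unknown. With r = 1%, the chance of seeing no SAE rises from 0.151 under full capture to 0.625 when a quarter of events are captured.

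**The case against.** The strongest reply is that section 6.1 is open about its limits: it says why records were not sought and which outcomes are missing. That is true of the SAP, but nothing in it carries the caveat into the trial report.

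A reader might go further than the documents allow in two ways.

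- **That there is no source of SAE data.** The SAP names open-ended self-report, emails, phone calls, and questions on surgery and hospital stays. These are weak and cannot by themselves establish cause, but they exist.
- **That the report must show zero SAEs.** Excluding only planned surgery implies that other surgery or hospitalization could count, so an app-arm SAE remains possible. Nor does the SAP say that it will report none.

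Three further replies have some force. Who judges relatedness, and how, may be in the protocol, which is not at hand; the point therefore does not rest on the absence of an assessor. Severity and seriousness are separate scales, so the missing severe grade is a small gap of its own. The SAP's past tense suggests that collection is settled, so no revision can recover deaths or life-threatening events. Safety is also not a stated objective. That limits the weight of the point without removing it, since the plan still includes a safety analysis.

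**Conclusion.** The point holds in limited form. Three things follow from the text alone: the control-arm SAE count is zero by definition, the counts of death and life-threatening events are zero in both arms, and no adverse event can be graded severe. App-arm SAEs through prolonged hospitalization or disability can be recorded, with unknown completeness. A total of zero is therefore not guaranteed, but it would be largely uninformative.

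The size of the loss cannot be computed from the documents. The illustration depends on assumed values of r and c and shows only the direction. No bound on the SAE risk is offered, because capture is unknown and the scope of the admissions item is unsettled. The primary, secondary and cost-effectiveness analyses are unaffected. This should be corrected before the safety results are written up.

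**What to change.** In section 6.1:

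1. Define seriousness by outcome, among the events actually captured and in either arm. Record relatedness to the intervention as a separate item.
2. Reconcile section 6.1 with Table 1 on whether the admissions question covered all admissions or only those due to hand osteoarthritis, and label the results accordingly.
3. Tabulate by arm the hospital admissions and hand surgery collected at 3 and 6 months, with planned surgery on its own line. If the data do not separate planned from unplanned surgery, show all hand surgery on its own line and say so.
4. Allow a severe grade.
5. Require the report to state that deaths and life-threatening events were not ascertained, and not to claim that no SAEs occurred.

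The cost is revised wording and one more table from items already planned; no new data collection is needed. The safety statement becomes less favourable, and the table covers only what participants reported.
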